The essential components of a quality orthosis are comfort, efficiency and ease of fitting. Comfort is paramount, as it is directly related patient adherence to treatment. The effectiveness of orthotic treatment can be measured by a reduction in gonarthrosis symptoms or medication use, and potentially an increase in the patient's ability to perform problematic movements. The ease with which the orthosis can be fitted is a component that needs to be optimized, as the user-friendliness of the treatment is important to increase patient adherence to it. The system developed in partnership with Laboratoires Victhom for this project is designed to simplify orthosis fitting, while maintaining comfort and effectiveness.

Research objectives

The aim of this research is to compare two fastening systems for VKB, one consisting of Velcro straps and the other of 3D-printed straps with cable clamping.

With this research, we seek to answer the following questions:

- Is the new cable-tightened belt system as effective at controlling symptoms as the Velcro fastening system currently on the market?
- Is the new cable-tightened strap system more comfortable than the Velcro fastening system currently on the market?
- Does the new fastening system make it easier to install the brace than the one currently on the market?

Our hypotheses are that the new attachment system will be more comfortable and easier to install than the one currently on the market.

Financing

The project was funded by NSERC's *Strengthening College and Community Innovation* program in partnership with Laboratoire Victhom Inc.

Partner company

Laboratoire Victhom Inc.

[name], Vice-President, Research and Development

[name]

[contact]

[contact]

RESEARCH METHODOLOGY

Research location

On TOPMED's premises at [name], Collège Mérici, Quebec City. Impression taking, orthosis delivery and adjustments prior to the trial period will be carried out at the balance clinic ([name]).

Type of test

Repeated measurements on single-factor groups with crossover: Attachment system (2 conditions).

Measurement, assessment and data collection tools

Logbook :

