A new knee brace will be made for each participant. To this end, an impression and anthropometric measurements will be taken during the first meeting with the participant to obtain an orthosis fitted to the patient's leg. Once the orthosis has been assembled, the participant will return to the balance clinic to receive his or her new orthosis. In addition, 3 questionnaires will be completed (ISP + KOOS + PAd1 Satisfaction) and photos of the fitted leg will be taken

Following the delivery meeting, a 14-day wearing period begins. Each time the brace is adjusted at the participant's request, the counter for the adjustment period is reset to zero. This wearing period will always be performed using the Velcro fastening system currently available on the market.

Once the fitting period is over, the first trial meeting will take place(d1). The 1st attachment system (C1) will be installed on the participant's orthosis. The order of attachment system conditions is randomized for participants. In addition, 4 questionnaires will be completed (General Info + ISP + KOOS + PAd14

Satisfaction). A 5th questionnaire (Satisfaction C1j1) will be added if the participant's first trial condition is the cable-tightening attachment system. This questionnaire will be completed after a few minutes' wear of the brace. Photographs of the fitted leg will be taken with all brace systems used during the trial. Following the first trial meeting, the first 14-day trial period begins. During this period, the participant must fill in an electronic logbook on a daily basis.

When the first trial period is over, the second trial takes place (d14). The 1st attachment system(C1) is removed and the 2nd system(C2) is installed on the participant's orthosis. In addition, 4 questionnaires are completed (ISP + KOOS + Satisfaction C1d14 + Satisfaction C2d14). Photos of the fitted leg will be taken, with all attachment systems used during the session. Following this meeting, the second 14-day trial period begins. Again for this period, the participant will be required to complete an electronic logbook on a daily basis.

The third and final trial meeting will take place following the 2nd trial period. The brace will be collected during this meeting. In addition, 4 questionnaires will be completed (ISP + KOOS + C2d28 Satisfaction + Attachment System Comparison). Photos of the fitted leg will be taken during the meeting.

Impression appointment: 45-minute appointment at the clinic.

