Delivery meeting: 1 hour 45 minutes at the clinic. 3 questionnaires will be completed and photos of the fitted leg will be taken.

Adjustment meeting(s): These meetings are optional, will be held at the client's request and last a maximum of 45 minutes.

1st trial session: This session lasts 2 hours at TOPMED. If no change is made to the brace attachment system, 4 questionnaires will be completed. However, if the brace attachment system is changed during the session, 5 questionnaires will be completed. Photographs of the fitted leg will be taken.

2nd trial meeting: This meeting lasts 2 hours at TOPMED, with 4 completed questionnaires and verification of logbooks. Photos of the fitted leg will be taken.

3rd trial meeting: This meeting lasts 1 hour at TOPMED, with 4 completed questionnaires and verification of logbooks. Photos of the fitted leg will be taken. The orthosis will be picked up during this meeting.

PARTICIPATION OF LIVE HUMAN, ANIMAL OR MATERIAL PARTICIPANTS

10 adult participants will be recruited to test the different orthoses. Participants should have mainly worn an ODRA 2.0 orthosis to allow a shorter orthosis fitting period . Participants with lower-limb wounds should be excluded, as wearing the orthosis could aggravate these.

Participant inclusion criteria:

- Be 18 years of age or older;
- Have worn an ODRA 2.0 orthosis for an average of several hours a day over the past 6 months

Participant exclusion criteria:

- People with wounds on the lower limbs.

SCIENTIFIC JUSTIFICATION FOR USING LIVE SUBJECTS

The participation of human participants representative of the clientele is essential for the validation of the new cable-tightening fastening system. Participant feedback will provide us with essential information on the brace's ease of installation, comfort and symptom control, enabling us to confirm the desired properties and, if necessary, modify certain aspects to better match the needs and problems of the target clientele. In addition, the new attachment system needs to be tested on participants to measure the potential biomechanical effects of this new technology

RECRUITMENT

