Vichom Laboratories will contact identified customers to request their consent to share their personal information with the research team. If consent is obtained, the customer's full name and e-mail address will be transferred to TOPMED. These consenting customers will then be contacted by TOPMED with an offer to participate in the current project. Candidates may express their interest by writing to TOPMED. A member of the project team ([name]/[name]/[name], Orthotics-Prosthetics Research Professional) will be available to answer questions, assess eligibility, send documentation and/or set up a telephone appointment at a later date.

RISKS AND DRAWBACKS, AND PROPOSED MITIGATION MEASURES

An allergic skin reaction (redness) due to wearing the brace is a potential injury. The participant should stop wearing the brace, if necessary.

Bruises, corns, scratches and/or pain may appear on the fitted limb, due to poor orthotic fit or incorrect positioning. The orthotist will be present to ensure the best possible fit of the orthosis during the session. Injuries due to appliance breakage are possible.

ADVANTAGES AND BENEFITS

No immediate benefit for participants, except the benefit of trying a new orthosis that could improve their quality of life. The advantage of their participation is that it will provide empirical data on orthosis wear. This is an advantage for Laboratoire Vichom Inc.

FREE AND INFORMED CONSENT

The Information and Consent Form (ICF) will be e-mailed to them once the candidate has shown interest by contacting us again. A period of two (2) weeks will be allowed for reading and reflection. Upon receipt of the signed CIF, the first meeting will be scheduled.

Participants may terminate their participation at any time without negative consequences or prejudice and without having to justify their decision. In this case, participants must inform the responsible researcher or a member of the research team. Thereafter, all material allowing the identification of the participant and the data provided will be destroyed, unless the participant authorizes the researcher to use them for the research despite the withdrawal. In this case, they will be preserved according to the measures described below, which will be applied to all other participants.

CONFIDENTIALITY AND PROTECTION OF PERSONAL INFORMATION

Information collected from questionnaires, photos, logs, anthropometric measurements, videos and gait

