pattern analysis data is confidential and will be used only for the purposes of this research project, unless otherwise agreed by the participant. All data collected, notes, photos and computer recordings are encrypted on servers. Unless required by law, no information that could directly or indirectly reveal your identity will be disseminated or published without your prior explicit consent.

All questionnaires and digital logs have been created using the Lime Survey platform. The information processed is hosted in Canada on the platform's encrypted servers (Secure Socket Layer procedure), which comply with the RGPD standard.

Data will be stored in coded form for a period of five (5) years, then anonymized in a database for retention for a period of ten (10) years for statistical reference purposes.

CONTINUOUS EXAMINATION

Should any inconvenience arise following the completion of the prototype validation test, participants will be promptly notified.

DISSEMINATING RESULTS

No disclosure to patients will be made following the trials.

Results will not be published.

COMPENSATION

If necessary, a parking sticker will be provided to participants during their visit. A compensation of \$50 will be given for their participation in each meeting of the validation protocol. The total amount awarded may not exceed \$350, equivalent to the full protocol with 2 adjustment meetings. The first payment will be made after the first trial meeting. The remainder of the amount will be distributed at the last meeting or when the participant chooses to end his or her participation.

RESPONSIBILITY

The legal rights of each participant will be maintained.

PROTOCOL SEQUENCE

First contact

Email to candidates

- *0241_VICD_Courriel_Recruitment*

Admission

Demonstrate interest by responding to e-mail/phone call

Sending documents and explanations :

- *0241_VICD_CourrielFIC*
- *0241_VICD_Consent_form*

Receipt of signed consent

Telephone contact for impression appointment

COVID call

Self-evaluation confirmation 24 hours before each meeting.

Impression meeting

45-minute meeting at the balance clinic

Anthropometric measurements of the thigh and digital impression taken

Delivery meeting

Meeting at the Balanced Clinic 1h45

Questionnaires: Satisfaction + KOOS + ISP

- *0241_VICD_Questionnaire_Satisfaction*
- *0241_VICD_Questionnaire_KOOS*
- *0241_VICD_Questionnaire_ISP*

Photos

Adjustment meeting

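### Does destroying a leaver's data, unless the leaver authorises their use, damage the ten-person crossover comparison?

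*Protocol*

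**What the plan says.** The rule stands in the protocol under Free and informed consent. A participant may stop at any time, without prejudice and without giving a reason. Then: "Thereafter, all material allowing the identification of the participant and the data provided will be destroyed, unless the participant authorizes the researcher" to use them in spite of the withdrawal. Authorised material is preserved under the same measures as for all other participants. Under Confidentiality and protection of personal information these begin: "Data will be stored in coded form for a period of five (5) years".

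Leaving is not silent. The same section says: "In this case, participants must inform the responsible researcher or a member of the research team". Under Compensation: "The remainder of the amount will be distributed at the last meeting or when the participant chooses to end his or her participation".

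The setting is a randomised-order, two-condition crossover: "10 adult participants will be recruited to test the different orthoses". Under State of knowledge and project relevance the protocol says: "Comfort is paramount, as it is directly related patient adherence to treatment". The forms on file when a person leaves follow from Estimated duration of participants' activities. At the second trial meeting, "4 questionnaires are completed (ISP + KOOS + Satisfaction C1d14 + Satisfaction C2d14"). At the first trial meeting, "A 5th questionnaire (Satisfaction C1j1) will be added" when the cable system comes first.

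**The concern.** The default covers outcome data as well as identifying material, and keeping them needs a positive act by the leaver. No step in the protocol says that anyone asks for it. Comfort is one of the three research questions and the protocol ties it to adherence, so a reader may suspect that people leave because of discomfort. Those people would then disappear from the record.

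With 10 participants each erased person is 10% of the sample, and no later analysis can recover destroyed records. If leavers were mostly people unhappy with one system, the remaining data would flatter that system.

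**Working it through.** The protocol states no withdrawal rate, authorisation rate, effect size or standard deviation, so there is no figure of its own to reproduce. Three checks apply.

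**1. Does the text contradict itself or block retention?**

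- The consent section sets destruction as the default and, in the same sentence, gives the exception. Authorised data may be used for the research and are stored as for everyone else. Nothing elsewhere in the protocol conflicts with this.
- An authorisation route implies that someone seeks the authorisation. The natural place is the consent form, which is listed by file name under Protocol sequence and is not among the documents at hand. Its silence cannot be assumed. The leaver must contact the team in any case, so there is an occasion to ask.
- The clause does not forbid a non-identifying count of withdrawals. Reporting that count and analysing authorised partial data are matters for an analysis plan or study report.
- The comfort sentence concerns adherence to treatment. A person who wears the brace less but stays in the study does not trigger the clause.

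**2. What does the clause itself remove?**

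Count the KOOS, Satisfaction and Comparison forms completed after the first randomised system is installed, leaving out the psychological inventory (ISP) and the run-in forms:

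- First meeting: 1 Satisfaction form, only if cable comes first.
- Second meeting: KOOS + 2 Satisfaction = 3.
- Third meeting: KOOS + Satisfaction + Comparison = 3.
- Total: 3 + 3 = 6 (Velcro first) or 1 + 3 + 3 = 7 (cable first).

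| Non-authorising leaver | Removed by the clause | Never collected under any rule | Logbook days removed |
|---|---|---|---|
| In period 1 | 0 of 6 or 1 of 7 | 6 | 0 to 14 of 28 |
| In period 2 | 3 of 6 or 4 of 7 | 3 | 14 to 28 of 28 |

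For 0, 1, 2 or 3 such period-2 leavers (assumed), end-of-first-condition KOOS and Satisfaction remain for 10, 9, 8 or 7 people. If every leaver authorises, the clause removes nothing.

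**3. What is that worth in precision?**

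Assume a 5:5 allocation (the ratio is not stated), leavers in period 2 and a within-person correlation ρ of 0.3 to 0.7. Let S be the sum of 1/n over the two sequences: S_all for all who started, S_c for those who finish. With period and treatment effects in the model:

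- data destroyed: Var = σ²(1 − ρ)S_c / 2
- period-1 data kept: Var = σ² / [1/S_all + (1 + ρ)/((1 − ρ)S_c)]

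With no leavers, S_all = S_c = 1/5 + 1/5 = 0.4 and the two agree. At ρ = 0.5 both give 0.1σ².

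Example with one leaver at ρ = 0.5: S_c = 1/5 + 1/4 = 0.45.

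- Destroyed: 0.5 × 0.45 / 2 = 0.1125.
- Kept: 1/(2.5 + 3/0.45) = 0.1091.
- Ratio of standard errors: √(0.1091/0.1125) = 0.985, so keeping the data gains 1.5%.

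| Leavers by sequence | S_c | SE vs no leavers, kept | SE vs no leavers, destroyed | Gain from keeping |
|---|---|---|---|---|
| 0 and 1 | 0.450 | 1.038 to 1.051 | 1.061 | 0.9% to 2.1% |
| 1 and 1 | 0.500 | 1.072 to 1.098 | 1.118 | 1.8% to 4.1% |
| 0 and 2 | 0.533 | 1.093 to 1.127 | 1.155 | 2.4% to 5.4% |

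Most of the rise in standard error comes from the unfinished second period, which no retention rule repairs. A complete-pairs analysis gains nothing at all from keeping the data.

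**The case for a change.** The strongest reply is about selection, not precision. Withdrawals are plausible: at an assumed 10% chance per person, at least one of 10 leaves with probability 1 − 0.9^10 = 65%. If 7 of 10 were comfortable on cable and the other 1, 2 or 3 were erased, the record would show 7/9 = 78%, 7/8 = 88% or 7/7 = 100% instead of 70%. Destruction is irreversible, and asking for permission costs little.

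The count above also leaves out run-in forms, which the clause destroys too. A cable-first person who leaves in period 2 has Velcro KOOS and Satisfaction from the end of the run-in and cable KOOS and Satisfaction from the end of period 1. That is a within-person contrast, and it is lost.

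The irreversibility stands, and so does the run-in point, though that contrast is in fixed order and is not the randomised comparison. The percentages do not establish a bias. They use a yes/no comfort endpoint that the protocol does not define. They also need every uncomfortable person both to leave and to withhold authorisation, and no passage supports either link. They charge the whole loss to the clause as well, although a Velcro-first person who leaves in period 2 never supplies an end-of-period cable outcome.

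Spelling out that permission is requested would be a reasonable courtesy to the reader. Wishing for it does not make the stated rule wrong.

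**Conclusion.** The concern does not hold. The protocol makes a recognisable ethical choice, states it clearly and provides for retention. The only change that would alter the rule itself, retention unless the leaver objects, is a matter for the ethics committee and not a statistical correction.

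The possible loss is real but conditional, and it is zero if leavers authorise. Otherwise it is at most 3 of 6 or 4 of 7 post-randomisation outcome forms per leaver, plus the logbook days and run-in forms on file. On the assumptions used (5:5 allocation, one or two leavers in period 2, correlation 0.3 to 0.7) retention is worth about 1% to 5% of the standard error. The direction and size of any bias cannot be derived from the document.

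The conclusion treats the unseen consent form as the place where permission is sought. If that form did not ask, this would be a gap in the consent procedure. It would still not show that the rule in the protocol gives a wrong result.
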